#### 3.2. Secondary Endpoints

The secondary endpoints for the study are:

- Comparison of primary and secondary efficacy parameters between doses
- Incidence of adverse events (AEs), serious adverse events (SAEs), and changes in laboratory test results
- Bone marrow improvement:
  - Bone marrow response rate at weeks 12, 24, and 36
  - Duration of bone marrow response
- Hemoglobin improvement

Baseline Status	Categories of Hemoglobin Improvement
Subjects who are transfusion dependent ( $\geq 2$ units PRBC every 4 weeks for 12 weeks prior to or after C1D1), regardless of baseline hemoglobin level	Percent of subjects with Red cell transfusion independence (no transfusions for $\geq 12$ consecutive weeks)  OR  50% reduction in RBC transfusions for $\geq 12$ consecutive weeks
Subjects with baseline hemoglobin $< 100$ g/L AND Not transfusion dependent	Percent of subjects with $\geq 10$ g/L and $\geq 20$ g/L increase in hemoglobin for $\geq 12$ consecutive weeks without transfusions

- Platelet improvement

Baseline Status	Categories of Platelet Improvement
Subjects who are transfusion dependent ( $\geq 2$ platelet transfusions in any 12 weeks prior to or after C1D1), regardless of baseline platelet level	Percent of subjects with: Platelet transfusion independence (no transfusions for $\geq 12$ consecutive weeks)  OR

Platelet transfusion = either 1 unit apheresed (single donor) platelets or 4-8 units pooled random donor platelets	50% reduction in platelets transfusions for $\geq$ 12 consecutive weeks
Subjects with $25 < \text{baseline platelets} < 50 \times 10^9/\text{L}$  AND Not platelet transfusion dependent	Percent of subjects with: Doubling of baseline platelet count for $\geq$ 12 consecutive weeks without platelet transfusions  OR  Platelet count $> 50 \times 10^9/\text{L}$ for $\geq$ 12 consecutive weeks without platelet transfusions,
Subjects with baseline platelet count $< 25 \times 10^9/\text{L}$  AND Not platelet transfusion dependent	Percent of subjects with: Doubling of baseline platelet count for $\geq$ 12 consecutive weeks without platelet transfusions  OR  Platelet count $> 25 \times 10^9/\text{L}$ for $\geq$ 12 consecutive weeks without platelet transfusions

- Hematologic improvement

Baseline Status	Categories of Hematologic Improvement

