2.2.2 Secondary Efficacy Endpoints

The secondary efficacy endpoints are as follows for:

Stage 1:

- Bone Marrow MF grade shifts relative to baseline over time
- Modified Myeloproliferative Neoplasm-Symptom Assessment Form Total Symptom Score (MPN-SAF TSS) changes from baseline over time

Stage 2:

- Bone Marrow improvement:
 - Bone marrow (BM) response rate (MF Grade) at each visit (reduction of 1 grade versus baseline)
 - Duration of BM response defined for responding subjects as time from first decrease from baseline of one grade to time of return to baseline levels. If no return to baseline levels or worse than baseline then duration will be censored at the last BM assessment.
- Hemoglobin improvement (number and percentage of subjects):
 - For red blood cell transfusion dependent subjects at baseline (at least 2 units every 4 weeks for 12 weeks prior to Cycle [C]1Day [D]1), improvement is defined as either:
 - 1) absence of any packed red blood cells (PRBC) transfusion during any consecutive 12 weeks interval with hemoglobin level of ≥80g/L

OR

- 2) at least a 50% reduction in PRBC transfusions for 12 consecutive weeks with hemoglobin level of ≥80g/L
- For red blood cell transfusion independent subjects improvement is defined as:
 - ≥10 g/L increase in hemoglobin level for 12 consecutive weeks without transfusions
- Platelet improvement (number and percentage of subjects)

- For transfusion dependent subjects at baseline, improvement is defined as either:
- 1) becoming transfusion independent for 12 consecutive weeks

OR

- 2) reduction in transfusions need ≥50% from baseline for 12 consecutive weeks
- For transfusion independent subjects with baseline platelet count below 100^9/L, improvement is defined as:
 - ≥50% increase in the number of platelet for 12 consecutive weeks or normalization of platelet count (above lower limit normal)
- Symptom improvement:

Percent of subjects with 50% reduction in MPN-SAF TSS from baseline over time(Tefferi 2013)

• Percent of subjects with complete response, partial response, clinical improvement, stable disease and progressive disease according to IWG-MRT criteria.

2.2.3 Exploratory Efficacy Endpoints

The exploratory efficacy endpoints are as follows for:

Stage 1:

- Bone marrow biopsy results for:
 - Myeloblasts (%), at each time point and change from baseline
 - Cellularity (%), at each time point and change from baseline
 - Collagen and reticulin grade shifts relative to baseline over time

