The platelet improvement analyses will be presented by platelet levels (subjects with platelet <50 x10^9/L at baseline and subjects with platelet <25 x10^9/L at baseline)

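### SAP 2.2.2 and protocol 3.2 score Stage 2 platelet improvement by different rules, and neither rule contains the other

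*SAP*

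**What the plan says.** Protocol 3.2, repeated in the protocol synopsis and in SAP Appendix 3, puts subjects who are not platelet-transfusion dependent into two baseline classes: between 25 and 50 x 10^9/L, and below 25. In both classes "Doubling of baseline platelet count" is one route to success. The other is a count above 50 in the upper class, or above 25 in the lower class. Either must hold for at least 12 consecutive weeks with no platelet transfusion. A subject at 50 or more who is not transfusion dependent is not scored on the count.

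SAP 2.2.2 has one class for these subjects: "For transfusion independent subjects with baseline platelet count below 100^9/L, improvement is defined as" a rise of at least 50% over 12 consecutive weeks, or normalization above the lower limit of normal. It does not require the period to be free of platelet transfusions, although the corresponding hemoglobin item in the same section does.

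SAP 4.4.5 adds a presentation by baseline level: "subjects with platelet <50 x10^9/L at baseline and subjects with platelet <25 x10^9/L at baseline". It does not mention the success rule.

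**The concern.** The SAP body changes three parts of a named secondary endpoint: who is scored, what counts as success, and whether transfusions are allowed during the response. It does not flag or explain the change. SAP Appendix 3 still carries the protocol rule, so the SAP holds two definitions of one endpoint.

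A rule that was uniformly stricter or uniformly broader would at least bound the protocol rate from one side. If subjects can switch both ways, the SAP rate says nothing definite about the protocol rate. The definition also feeds other outputs. SAP 4.4.2 computes duration of improvement in thrombocytopenia among subjects scored as improved, and SAP 4.8 repeats the secondary endpoints on the extension population.

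**Working it through.** The documents give no response rate, power or sample size for this endpoint, so there is no figure to reproduce. The check sets the two rules against each other.

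**Inputs.** Let b be the baseline and f the count held throughout the 12 weeks, in x 10^9/L, with no transfusions.

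- Protocol 3.2: if 25 < b < 50, success is f ≥ 2b or f > 50. If b < 25, success is f ≥ 2b or f > 25.
- SAP 2.2.2: if b < 100, success is f ≥ 1.5b or f > LLN. The printed 100^9/L is read as 100 x 10^9/L. The lower limit of normal (LLN) is not given and is assumed to be 100 or more.

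**Effective thresholds.** In the upper protocol class doubling is redundant, because 2b > 50 whenever b > 25. In the lower class doubling is the easier route only while 2b < 25, that is b < 12.5. The SAP's 50% line meets the protocol line where 1.5b = 25, so b = 25/1.5 = 16.7, and where 1.5b = 50, so b = 50/1.5 = 33.3.

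| Baseline b | Protocol needs | SAP 50% rule needs | SAP is |
|---|---|---|---|
| below 12.5 | 2b | 1.5b | more lenient |
| 12.5 to 16.7 | above 25 | 1.5b, at most 25 | more lenient |
| 16.7 to 25 | above 25 | 1.5b, from 25 to 37.5 | stricter |
| 25 to 33.3 | above 50 | 1.5b, from 37.5 to 50 | more lenient |
| 33.3 to 50 | above 50 | 1.5b, from 50 to 75 | stricter |

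**Worked cases.**

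| b to f | f/b | Protocol | SAP |
|---|---|---|---|
| 10 to 15 | 1.5 | fails (needs 20) | succeeds |
| 20 to 26 | 1.3 | succeeds (above 25) | fails (needs 30) |
| 30 to 45 | 1.5 | fails (needs above 50) | succeeds |
| 40 to 52 | 1.3 | succeeds (above 50) | fails (needs 60) |
| 80 to 120 | 1.5 | not scored | succeeds |

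**Does normalization rescue the lost protocol successes?** Those cases lie where the protocol is met and f < 1.5b. Since b < 50, f is below 1.5 x 50 = 75, which is under any LLN of 100 or more. So it does not, for a count held at one level. The SAP wording leaves open whether normalization must itself last 12 weeks.

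**Both directions on a grid.** Over integer baselines 5 to 49 (excluding 25) and sustained counts 5 to 100, there are 44 x 96 = 4,224 combinations. Of these, 224 succeed under the protocol and fail under the SAP, and 100 do the reverse. This shows only that both kinds of disagreement exist. The cells are not weighted by how often patients fall in them.

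**Population.** Protocol 10.2 requires at least 50% of subjects to have platelets below 50. At 84 planned, the anemia-alone stratum can therefore hold at most 84 − 42 = 42. Only those with platelets from 50 up to 100 who are not transfusion dependent would newly enter the SAP's count-based class.

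**The case against.** The other side has several good points.

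- **The population change is partly handled.** SAP 4.4.5 requires results for baselines below 50 and below 25. This stands, but those displays keep the SAP success rule, and the two-way switching occurs entirely below 50.
- **The endpoint's weight is limited.** It is one of several secondary endpoints. SAP 4.4.2 names no between-arm test for it, and protocol 10.6.1.3.4 makes such comparisons unadjusted and to be read with caution. The primary endpoint and its 10% rule are untouched. All of this stands and bears on severity.
- **Changes may be documented elsewhere.** Protocol 10.3.1 sends changes of method to the clinical study report. That softens the complaint about a missing reason, but it does not resolve two definitions inside one SAP.

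Three stronger readings are tempting, and the documents do not support them.

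- A reader might infer that the trial defines thrombocytopenia as below 50 throughout. That figure is the eligibility and stratification cut-off and the bound of the protocol's count-based classes. The secondary objective gives no number. Protocol 3.2 also scores transfusion-dependent subjects at any platelet level, and 100 appears in the IWG-MRT complete-response criteria and in an exploratory endpoint.
- A reader might infer that half the subjects would wrongly enter the rate. Half is a ceiling on the anemia-alone stratum. Anyone in it at 100 or above stays outside the SAP's count-based class.
- A reader might infer that the rule was introduced after the Stage 2 data were seen. SAP section 1 says that this SAP preceded the final extension lock and that a Stage 2 SAP version 2.0 was signed before the Stage 2 primary lock. Version 2.0 was not among the documents reviewed, so it cannot be said which of the two introduced the rule.

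**Conclusion.** The point holds as a conflict of definitions. SAP 2.2.2 and protocol 3.2 give incompatible success rules for the same secondary endpoint, and the displays in SAP 4.4.5 restore the protocol's population below 50 but not its success rule. As written, the SAP rate does not answer the protocol endpoint and does not bound it.

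On the 50% criterion the SAP is more lenient below about 16.7 and from 25 to 33.3, and stricter from about 16.7 to 25 and from 33.3 to 50. That result does not depend on how 100^9/L is read. The statement that normalization rescues none of the lost successes assumes a lower limit of normal of 100 or more. How many subjects are reclassified, and which way the rate or the contrast between doses would move, cannot be computed from the documents.

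**What to change.** In SAP 2.2.2, report the protocol 3.2 rate as the secondary endpoint for subjects not dependent on platelet transfusions: baseline below 50; doubling, or exceeding 50 or 25 according to class; at least 12 consecutive weeks; no platelet transfusions in that period. Assign a baseline of exactly 25, which falls in neither protocol class, to one of them.

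Keep the rule of a 50% rise or normalization as a supportive analysis, labelled as differing from the protocol. State whether it was already in Stage 2 SAP version 2.0, correct the unit to 100 x 10^9/L if that is what is meant, and say whether normalization must last 12 weeks.

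The cost is SAP wording, one additional derived variable and one table. Platelet counts and transfusion records are already collected at every cycle.

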Not transfusion dependent	consecutive weeks without transfusions
Platelet improvement:	
Baseline Status	Categories of Platelet Improvement
Subjects who are transfusion dependent (≥ 2	Percent of subjects with:
platelet transfusions in any 12 weeks prior to	Platelet transfusion independence (no
or after C1D1), regardless of baseline platelet	transfusions for ≥ 12 consecutive weeks)
level	
	OR
Platelet transfusion = either 1 unit apheresed	
(single donor) platelets or 4-8 units pooled	50% reduction in platelets transfusions for
random donor platelets	≥ 12 consecutive weeks
Subjects with 25 < baseline platelets < 50 x	Percent of subjects with:
10^{9} /L	Doubling of baseline platelet count for ≥ 12
AND	consecutive weeks without platelet
Not platelet transfusion dependent	transfusions
	OR
	Platelet count $> 50 \times 10^9 / L \text{ for } \ge 12$
	consecutive weeks without platelet
	transfusions
Subjects with baseline platelet count $< 25 \text{ x}$	Percent of subjects with:
$10^{9}/L$	Doubling of baseline platelet count for ≥ 12
AND	consecutive weeks without platelet
Not platelet transfusion dependent	transfusions
	9.00
	OR
	Platelet count > 25 x 10^9 /L for ≥ 12
	consecutive weeks without platelet
	transfusions
Hematologic improvement:	,
	Catagories of Hamatalagia Impunyariant
Baseline Status Subjects with both Hemoglobin < 100 g/L	Categories of Hematologic Improvement Percent of subjects who have EITHER
and Platelets < 50 x 10 ⁹ /L	Hemoglobin improvement OR Platelet
and I fatelets > 50 x 10 /L	
	improvement as described above and no
	worsening of hemoglobin or platelets from baseline
Subjects with only Hemoglobin < 100 g/L	Percent of subjects who have Hemoglobin
Subjects with only Hemogroum > 100 g/L	improvement as described above
	AND
	Did not develop platelets < 50 x 10 ⁹ /L
	Did not develop plateiets > 30 x 10 /L

Subjects with only Platelets $< 50 \times 10^9/L$	Percent of subjects who have Platelet
	improvement as described above
	AND
	Did not develop Hemoglobin < 100 g/L or
	new transfusion dependence

- Symptom improvement:
 - Percent of subjects with 25% and 50% reduction in MPN-SAF Total Symptom Score from baseline at Week 36
 - o Mean change from baseline in EORTC QLQ-C30 at 36 weeks
- Duration of all improvement parameters listed above
- Percent of subjects with complete response, partial response, clinical improvement, stable disease, and progressive disease according to IWG-MRT criteria (Tefferi 2013, Appendix B)

Exploratory:

- Bone marrow

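### SAP 2.2.2 leaves the transfusion-free condition out of platelet improvement for transfusion-independent subjects, and does not make clear whether normalization must last 12 weeks

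*SAP*

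**What the plan says.** Protocol 3.2 gives two rows for subjects who are not platelet transfusion dependent, with baseline counts between 25 and 50 or below 25 x 10^9/L. Each row offers two routes to improvement: doubling of the baseline count, or a count above 50 (above 25 in the lower row). Each route must hold for at least "12 consecutive weeks without platelet transfusions". SAP Appendix 3 reprints the same rows and the same condition ("consecutive weeks without platelet", with the phrase broken across table lines).

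The Stage 2 rule in SAP 2.2.2 is different. For transfusion-independent subjects with a baseline count below a limit printed as 100^9/L, which I read as 100 x 10^9/L, improvement is a 50% or greater "increase in the number of platelet for 12 consecutive weeks or normalization of platelet count (above lower limit normal". Transfusions are not mentioned.

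The hemoglobin rule for transfusion-independent subjects in the same section does keep the condition: "increase in hemoglobin level for 12 consecutive weeks without transfusions". So does the exploratory platelet endpoint in SAP 2.2.3, a rise from below 50 to at least 100 at Week 36.

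**The concern.** A platelet count can rise because platelets were transfused. That is why the protocol requires the qualifying period to be transfusion-free, and the SAP bullet has lost the requirement. Calling a subject transfusion independent does not restore it: the label says who enters the rule, while the protocol's condition governs what happens during the 12 weeks being credited.

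The second weakness is grammatical. The 12-week phrase stands before the word or, so it clearly governs the 50% route and only arguably governs normalization. Two programmers could code this endpoint differently, and both could point to the text.

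At stake is a named secondary endpoint. The effect on thrombocytopenia is a stated secondary objective (protocol 2.2), and at least half of the Stage 2 population is to have baseline thrombocytopenia (protocol 10.2). SAP 4.8 also carries the secondary endpoints into the open-label extension where applicable.

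**Working it through.** The documents give no sample size, power or expected rate for platelet improvement, so there is no planned figure to reproduce. The check is a comparison of the rules, followed by a count of scheduled visits.

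**Routes to improvement for subjects who are not transfusion dependent**

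| Source | Routes | Transfusion-free stated | Clearly tied to 12 weeks |
|---|---|---|---|
| Protocol 3.2, platelets | 2 rows x 2 = 4 | 4 of 4 | 4 of 4 |
| SAP Appendix 3, platelets | 2 rows x 2 = 4 | 4 of 4 | 4 of 4 |
| SAP 2.2.2, platelets | 2 | 0 of 2 | 1 of 2 |
| SAP 2.2.2, hemoglobin | 1 | 1 of 1 | 1 of 1 |

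**Whether another SAP section restores the condition.** SAP 4.4.2 says how duration of improvement is measured, and SAP 4.4.5 adds a display by baseline platelet level. Neither mentions transfusions during the qualifying period. SAP 4.4.2 does measure duration from a first 12-week period of improvement. That presupposes that every improvement lasts 12 weeks, but it does not say that normalization must.

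**How many transfusions the SAP wording tolerates.** The protocol's routes tolerate none. The SAP answer depends on what independent means, and the platelet rule does not define it:

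- If it carries the meaning that protocol 3.2 gives to becoming independent (no transfusions for 12 weeks) and is applied to the qualifying period: 0.
- If it is the complement of the protocol's definition of dependence, at least two "platelet transfusions in any 12 weeks prior to or after C1D1": 2 - 1 = 1 in any 12 weeks.
- If it is a status fixed at baseline: no stated limit on study.

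The SAP does not choose among these, so none of the three can be offered as the size of the problem.

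**What the duration ambiguity means in visits.** Protocol Appendix A schedules a blood count on Day 1 of Cycles 2 to 9, which is 8 counts, and on Cycle 9 Day 29, which is 1. That makes 8 + 1 = 9 post-baseline counts to Week 36. If normalization has no duration, any 1 of the 9 is enough. If it must last 12 weeks at 4-week spacing, it needs 12/4 = 3 consecutive counts when each count stands for its cycle, or 12/4 + 1 = 4 when the first and last count must be 12 weeks apart. The documents do not say which convention applies.

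**The case against.** The strongest reply is that the SAP is unclear rather than permissive. The words at baseline belong to the dependent rule ("For transfusion dependent subjects at baseline, improvement is defined as either"). In the independent rule, baseline qualifies the platelet count. A reader might infer that the SAP allows unlimited transfusions in the independent group, but that takes a phrase from one bullet and applies it to another. Given how the protocol describes independence, a reading that allows no transfusions in the qualifying period is also open. This stands, and it is why no transfusion limit is claimed here. It does not remove the omission: the condition is written out in the protocol, in Appendix 3 and in the neighbouring hemoglobin rule, and it is absent here.

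A reader might also infer that the SAP means to accept a single normal count. SAP 4.4.2 makes that the less natural reading. It remains the literal one and should be closed off.

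A third tempting step is to import the protocol's full definition of dependence, which counts transfusions after Cycle 1 Day 1 as well as before. That would do harm. Take a subject with no transfusions before treatment and none in Weeks 1 to 12, who then deteriorates and needs two in Weeks 25 to 36. That subject becomes dependent by a post-randomization event and, read literally, has met the 12 weeks without transfusion that count as improvement. The SAP's other dependent route, a 50% or greater reduction from baseline, would have no usable baseline for that subject.

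Finally, the SAP changed more than this condition. Doubling became a 50% rise, the 50 and 25 thresholds became the lower limit of normal, and the eligible baseline count widened. The table therefore compares conditions attached to two differently built endpoints. That is fair. It supports declaring those changes too, and does not justify dropping the transfusion condition.

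**Conclusion.** The point holds in a limited form. The omission is a matter of text and is certain. It looks like an oversight, since the parallel hemoglobin rule and the exploratory platelet endpoint keep the condition. The ambiguity about normalization is real, though SAP 4.4.2 points to 12 weeks. As written, the rule can class a transfusion-supported platelet count as improvement and, read literally, a brief normalization as well.

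The effect is confined to one secondary endpoint. The primary bone marrow response rate and the sample size are unaffected. How many subjects would be reclassified cannot be derived, and the documents give no platelet lower limit of normal. A reader might infer that the rule favours one dose or has inflated a result; nothing in the documents shows a difference between arms or any such result. SAP 1 refers to an earlier Stage 2 SAP (Version 2.0) that is not among the documents, so it is unknown whether that plan held a fuller rule. The present SAP defines the final analysis and does not refer to it for this endpoint. The rule should be settled before that analysis.

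**What to change.** Reword the SAP 2.2.2 bullet so that improvement is a 50% or greater increase from baseline, or normalization (above the lower limit of normal), each sustained for at least 12 consecutive weeks without platelet transfusions. Apply the condition with the transfusion diaries required by protocol 7.11.2.

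Keep platelet transfusion status defined at baseline, and do not adopt the part of the protocol's definition that counts transfusions after Cycle 1 Day 1. Once the qualifying period itself must be transfusion-free, that part is not needed.

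State in the SAP that the 50% rise, the lower limit of normal and the baseline limit of 100 all differ from protocol 3.2. Tabulate the protocol-defined response for non-dependent subjects alongside, using the protocol's rows (25 < baseline < 50 and < 25 x 10^9/L). A baseline of exactly 25 falls in neither row and needs a footnote.

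The cost is one bullet, a programming filter and one extra table. The platelet response rate may come out lower, by an amount that the documents do not allow anyone to estimate.
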